**11.1.3. Tertiary endpoints (Amended 29-MAY-2020)**

- Co-infections of RSV-LRTI with other respiratory viruses in infants, confirmed by PCR of nasal swabs in infants from birth up to 1 year of age:
  - Influenza A virus (Flu A)
  - Influenza B virus (Flu B)
  - Human Influenza A virus subtype H1 (Flu A-H1)
  - Human Influenza A virus subtype H3 (Flu A-H3)
  - Human Influenza A virus subtype H1pdm09 (Flu A-H1pdm09)
  - Human adenovirus (AdV)
  - Human metapneumovirus (MPV)
  - Human enterovirus (HEV)
  - Human parainfluenza virus 1 (PIV1)
  - Human parainfluenza virus 2 (PIV2)
  - Human parainfluenza virus 3 (PIV3)
  - Human parainfluenza virus 4 (PIV4)
  - Human bocavirus 1/2/3/4 (HBoV)
  - Human rhinovirus A/B/C (HRV)
  - Human coronavirus 229E (229E)
  - Human coronavirus NL63 (NL63)
  - Human coronavirus OC43 (OC43)

**CONFIDENTIAL**207636 (EPI-RSV-008 BOD)  
Protocol Amendment 4 Final

- Potential risk factors for pregnancy related and neonatal events of interest.
- Any further exploratory characterization of immune responses to RSV and/or other respiratory tract infections or infections of relevance to pregnant women and their newborns (based on maternal serum and cord blood) (*For example, levels of RSV-B neutralizing antibodies.*)
- *Episode(s) of RSV-LRTI/severe LRTI based on alternative case definitions, from birth up to 1 year of age.*

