**Tertiary**

- Co-infections of RSV-LRTI with other respiratory viruses in infants, confirmed by PCR of nasal swabs in infants from birth up to 1 year of age:
  - Influenza A virus (Flu A)
  - Influenza B virus (Flu B)
  - Human Influenza A virus subtype H1 (Flu A-H1)
  - Human Influenza A virus subtype H3 (Flu A-H3)
  - Human Influenza A virus subtype H1pdm09 (Flu A-H1pdm09)
  - Human adenovirus (AdV)
  - Human metapneumovirus (MPV)
  - Human enterovirus (HEV)
  - Human parainfluenza virus 1 (PIV1)
  - Human parainfluenza virus 2 (PIV2)
  - Human parainfluenza virus 3 (PIV3)
  - Human parainfluenza virus 4 (PIV4)
  - Human bocavirus 1/2/3/4 (HBoV)
  - Human rhinovirus A/B/C (HRV)
  - Human coronavirus 229E (229E)
  - Human coronavirus NL63 (NL63)
  - Human coronavirus OC43 (OC43)
- *Episodes of LRTIs/Severe LRTIs up to one year of age - using alternative case definitions*

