### 5.4. RSV infection (Amended 29-MAY-2020)

Nasal swabs will be analyzed by the sponsor for the presence of RSV A/B. A positive test result constitutes a case of RSV infection. Refer to Section 8.6.7.3.

**CONFIDENTIAL**207636 (EPI-RSV-008 BOD)  
Protocol Amendment 4 Final**Table 3 RTI/LRTI case definitions for data analysis**

RSV-RTI	Runny nose, OR Blocked nose, OR Cough AND Confirmed RSV infection 
RSV-LRTI	History of cough OR difficulty in breathing  AND SpO 2 < 95%  , OR RR increase  AND Confirmed RSV infection 
RSV-severe LRTI	Meeting the case definition of RSV-LRTI AND SpO 2 < 93%, OR lower chest wall in-drawing
RSV-very severe LRTI	Meeting the case definition of RSV-LRTI AND SpO 2 < 90%, OR inability to feed OR failure to respond / unconscious
RSV hospitalization	Confirmed RSV infection  AND Hospitalized for acute medical condition 
All-cause RTI	Runny nose, OR Blocked nose, OR Cough
All-cause LRTI	History of cough OR difficulty in breathing  AND SpO 2 < 95%  , OR RR increase 

Definitions based on [Modjarrad, 2016]

**RTI** = respiratory tract illness; **LRTI** = lower respiratory tract illness; **RR** = respiratory rate; **SpO2** = blood oxygen saturation by pulse oximetry.

 Based on history reported by parents/LARs and includes difficulty in breathing (e.g. showing signs of wheezing or stridor, tachypnoea, flaring [of nostrils], chest in-drawing, apnoea).

 For blood oxygen saturation (SpO2), the lowest value monitored will be used. In high altitudes (>2500m), SpO2 <92% for LRTI, <90% for severe LRTI, <87% for very severe LRTI.

 RR increase defined as:

- > 60/minute (< 2 months of age)
- > 50/minute (2 to < 12 months of age)
- > 40/minute (12 to 24 months of age)

 RSV infection confirmed on nasal swab positive for RSV A or B by quantitative reverse transcription polymerase chain reaction (qRT-PCR).

 RSV sampling and testing is described in Sections 8.6.7, 8.6.8 and 8.6.9.

 Hospitalization is defined as admission for observation or treatment based on the judgement of a health care provider

**CONFIDENTIAL**207636 (EPI-RSV-008 BOD)  

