Protocol Amendment 4 Final**Table 4 Alternative LRTI / Severe LRTI Case Definitions (Amended 29-MAY-2020)**

		Documented physical examination (PE) findings indicating lower respiratory tract involvement (at least one symptom)	Objective measures of clinical severity (at least one symptom)
LRTI	Confirmed RSV infection	Rhonchi Rales Crackles Wheeze	Increased respiratory rate (bpm) $\geq 60$ for < 2 mo $\geq 50$ for 2-6 mo  Hypoxemia: SpO2 <95% at <math>\leq 1800</math> meters SpO2 <92% at > 1800 meters  New onset apnea Nasal flaring Retractions Grunting
Severe LRTI	Confirmed RSV infection	Rhonchi Rales Crackles Wheeze	Hypoxemia  SpO2 <93% at <math>\leq 1800</math> meters SpO2 <90% at > 1800 meters  Acute hypoxic or ventilatory failure Dehydration due to respiratory distress requiring IV hydration Failure to respond or unconscious

Term not listed in the eCRF page in this study.Intercostal recession or chest wall indrawing are considered synonymous with and will be used as alternatives to the term "retractions," which is not listed in the eCRF page for this study.Acute hypoxic or ventilatory failure is not listed in the eCRF page for this study. Instead, the presence of either respiratory support excluding mechanical ventilation OR requirement for mechanical ventilation or both will be used.Dehydration due to respiratory distress requiring IV hydration is not listed in the eCRF page for this study. Skin turgor > 2 seconds or administration of IV fluid therapy will be used instead.

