**11.8. Analysis of tertiary objectives (Amended 29-MAY-2020)**

The following tertiary objectives analyses will be performed on infants within the PPS cohort, overall and possibly by region or other relevant grouping. *If there is difference of 5% or more between the number of participants in the enrolled set and the PPS, tertiary objectives analyses on the enrolled set will also be performed.*

- To describe co-infections of RSV-LRTI with other respiratory viruses in infants.
  - Considering all infants followed from visit 1-NB to visit 4-NB, the percentage of subjects with the occurrence of RSV-LRTI and having other respiratory viral co- infection identified by multiplex PCR, with exact 95% CI; classified by respiratory viruses.
- To estimate the association of RSV-LRTI in neonates/infants and the level of RSV neutralizing antibodies in cord blood.
  - Correlation analysis will be done comparing the levels of RSV antibodies present in cord blood and the presence or absence of RSV-associated LRTI, RSV-associated severe LRTI, and RSV-associated very severe LRTI in infants. Details will be described in the SAP.

The following tertiary objectives analyses will be performed on the PPS cohorts (maternal or infant as applicable) by country, region, or other relevant grouping:

**CONFIDENTIAL**207636 (EPI-RSV-008 BOD)  
Protocol Amendment 4 Final

- To determine risk factors for pregnancy-related and neonatal events of interest.
  - Risk factors will be described in the SAP.
  - The maternal events of interest will be described according to variables collected in the mother's clinical examination and obstetric risk factors. Frequency tables will be generated for categorical variables.
  - The neonatal events of interest will be described according to variables collected in the mother's clinical examination and obstetric risk factors. Frequency tables will be generated for categorical variables.
  - Furthermore, multiple variable analyses (such as multiple logistic regression for binary outcomes and multiple Poisson/negative binomial and/or other appropriate models for count outcomes) will be conducted to adjust for covariates of interest, provided there are sufficient numbers of events of interest.
- ***To determine the incidence of LRTIs/Severe LRTIs (using alternative case definitions)***
- If deemed necessary, to further characterize the immune responses to RSV and other infections in maternal subjects and infants (based on maternal serum and cord blood).

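### The alternative LRTI definition has no respiratory-rate cut-off after 6 months of age, yet its endpoint runs to 1 year, so non-severe incidence is understated in that period if Table 4 is applied as written

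*Protocol*

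**What the plan says.** Amendment 4 added a tertiary objective on LRTI and severe LRTI under alternative case definitions. Section 11.1.3 states the endpoint as "Episode(s) of RSV-LRTI/severe LRTI based on alternative case definitions, from birth up to 1 year of age", and the synopsis agrees: "Episodes of LRTIs/Severe LRTIs up to one year of age - using alternative case definitions". Section 11.8 gives the analysis in one line, "To determine the incidence of LRTIs/Severe LRTIs (using alternative case definitions", with no age limit.

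The definition is in Table 4 of Section 5.4. A case of alternative LRTI needs confirmed RSV infection, at least one chest finding, and at least one entry from a column headed "Objective measures of clinical severity (at least one symptom". In that column, increased respiratory rate means at least 60 per minute under 2 months of age and at least 50 per minute at 2-6 months. There is no later band. The other entries, such as "New onset apnea", carry no age limit. The severe LRTI row of Table 4 contains no respiratory-rate criterion at all.

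Table 3, which holds the main case definitions, has a rate cut-off of "> 50/minute (2 to < 12 months of age" and a further band beyond 12 months.

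**The concern.** The protocol itself fixes both the case definition and the age range of the endpoint, and the two do not fit. The missing band is therefore not detail that can simply wait for the SAP. Table 4 was adapted to this study in other respects: three of its footnotes name eCRF substitutes for terms that were not collected. The age bands were not extended to match the follow-up.

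Three readings of the results are exposed: the 12-month incidence of non-severe alternative-definition LRTI, any contrast between younger and older infants within Table 4, and any informal reading of Table 4 incidence next to Table 3 incidence over the first year. In addition, with no rule stated, whoever programs the endpoint must choose between no rate criterion, a carried-forward band and an age restriction, possibly after seeing data.

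**Working it through.** The plan gives no figure to reproduce here, and no sample-size or power figure depends on this point. The check has three parts.

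**1. One infant, both tables.** Take an RSV-positive infant with cough, wheeze, SpO2 97%, a raised respiratory rate and no other sign. The SpO2 value is above every threshold in either table. The cough meets the symptom requirement of Table 3, and the wheeze meets the chest-finding requirement of Table 4. Only the rate can then qualify the case.

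| Age (months) | Rate (/min) | Table 3 LRTI | Table 4 LRTI as written | Table 4 with the 2-6 month band carried forward |
|---|---|---|---|---|
| 1 | 65 | yes | yes | yes |
| 3 | 55 | yes | yes | yes |
| 5 | 55 | yes | yes | yes |
| 7 | 55 | yes | **no** | yes |
| 9 | 55 | yes | **no** | yes |
| 11 | 55 | yes | **no** | yes |

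If nasal flaring is added, the infant is a Table 4 case at every age. The loss is confined to infants for whom fast breathing is the only severity sign.

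**2. Share of follow-up without a cut-off.** Table 7 sets the 6-month visit at day 180 and the final visit at day 365.
- If the 2-6 month band ends at day 180: (365 - 180)/365 = 185/365 = 50.7%.
- If it includes the whole month in which the infant is 6 months old, so that it ends at 7 months: (12 - 7)/12 = 5/12 = 41.7%.

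**3. Size of the undercount.** Let *s* be the share of first-year alternative-definition LRTIs that would fall after 6 months if a cut-off existed, and *r* the share of those that would qualify by rate alone. The missed share is *s* × *r*. The documents give neither value. Purely as an assumption, *s* of 30-50% and *r* of 10-40% give from 0.30 × 0.10 = 3% to 0.50 × 0.40 = 20%. The width of that range shows that no single figure can be defended.

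**The case against.** The strongest reply is that Table 4 is silent after 6 months and does not say that rate is to be ignored. On that view the criterion is undefined, and the SAP could complete it. This stands in part: the downward bias follows only if the silence is applied literally. However, the protocol pairs this definition with a 12-month endpoint, and nothing in it says that another reading is intended.

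The effect is also narrow. One severity sign is enough, and hypoxemia, apnea, flaring, retractions and grunting remain available at every age. Severe LRTI is untouched. The endpoint is tertiary and descriptive, and the primary and secondary endpoints use other definitions. All of this stands.

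A reader might infer that the gap biases a planned comparison of the two definitions, and so the choice of definition for the pivotal trials. The documents do not support that. The objective, endpoint and analysis text ask only for incidence under the alternative definitions. Section 11.11.1, which mentions adjusting definitions for pivotal trials, concerns an optional interim analysis and names Table 3 only. The tables also differ by design, for example in required chest findings and altitude limits, so a difference between them would not come from the age band alone.

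**Conclusion.** The point holds in a limited form and is worth correcting. As written, the rate criterion cannot be met after 6 months, so non-severe alternative-definition LRTI incidence is understated over roughly 42-51% of follow-up. The direction is downward, on the assumption that Table 4 is applied literally. The number of missed cases cannot be derived from the documents, and the illustrative range above is not a finding.

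A reader might go further and conclude that the alternative-definition endpoint as a whole is unusable after 6 months. That does not follow: severe LRTI and LRTI qualifying by any other listed sign are counted correctly to 12 months. The consequence is moderate and is confined to one route into one non-severe tertiary endpoint.

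**What to change.** Reconcile Table 4 with Section 11.1.3, for analysis classification only and before the data are examined, by one of two routes:
- report non-severe alternative-definition LRTI incidence for birth to 6 months as the figure the definition fully covers; or
- state a labelled analysis cut-off for >6 to <12 months, for example the 2-6 month band carried forward, in line with Table 3's single band from 2 to <12 months.

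Under either route, state where the 2-6 month band ends and keep severe LRTI to 12 months. Present LRTI incidence by age (<2, 2-6 and >6-12 months) so that the affected period is visible. A blanket restriction of the whole endpoint to 6 months should be avoided, because it would discard valid later cases.

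The cost is a wording change and one stratified table. No new data are needed: respiratory rate is recorded at assessment visits (Section 8.6.7.2), and age at LRTI is already derived in months (Section 11.4).

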## 11.2. Determination of sample size

The target will be to enroll up to approximately 200 to 300 eligible subjects (pregnant women) by country. Subjects may drop-out from the study due to a variety of reasons, e.g. migration from the study area. Assuming a drop-out rate of about 10% during the course of follow-up, there will be up to approximately 180 to 270 evaluable subjects by country.

Considering a sample size of up to approximately 180 to 270 evaluable subjects by country, [Table 17](#) illustrates the precision (exact 95% confidence interval [CI]) one can get on the percentage of subjects with maternal, fetal and neonatal events of interest. Precision (exact 95% CI) has also been computed for a sample size of 270, 180 and 100 evaluable subjects for estimate by study site.

The percentages of subjects with maternal, fetal and neonatal events of interest for the primary objectives are expected to range from 0 to 35%.

**Table 17 Precision (exact 95% confidence interval) on the percentage of subjects with maternal, fetal and neonatal events of interest for sample size of 270, 180 and 100 subjects**

% 35 30 25 20 15 10 5 3 1 0	270 subjects			180 subjects			100 subjects		
	N 94.5 81 67.5 54 40.5 27 13.5 8.1 2.7 0	Lower 29.3 24.6 19.9 15.4 11 6.7 2.7 1.3 0.2 0.2 0	Upper 41 35.8 30.6 25.3 19.8 14.2 8.3 5.8 3.1 1.4	N 63 54 45 36 27 18 9 5.4 1.8 0	Lower 28.1 23.4 18.9 14.4 10.1 15.3 2.3 1 0.1 0	Upper 42.4 37.3 32 26.6 21.1 15.3 9.3 6.8 3.9 2	N 35 30 25 20 15 10 5 3 1 0	Lower 25.7 21.2 16.9 12.7 8.6 4.9 1.6 0.6 0 0	Upper 45.2 40 34.7 29.2 23.5 17.6 11.3 8.5 5.4 3.6
		limit limit limit limit limit limit limit limit limit limit limit	limit limit limit limit limit limit limit limit limit limit limit		limit limit limit limit limit limit limit limit limit limit limit				
35	94.5	29.3	41	63	28.1	42.4	35	25.7	45.2
30	81	24.6	35.8	54	23.4	37.3	30	21.2	40
25	67.5	19.9	30.6	45	18.9	32	25	16.9	34.7
20	54	15.4	25.3	36	14.4	26.6	20	12.7	29.2
15	40.5	11	19.8	27	10.1	21.1	15	8.6	23.5
10	27	6.7	14.2	18	6	15.3	10	4.9	17.6
5	13.5	2.7	8.3	9	2.3	9.3	5	1.6	11.3
3	8.1	1.3	5.8	5.4	1	6.8	3	0.6	8.5
1	2.7	0.2	3.1	1.8	0.1	3.9	1	0	5.4
0	0	0	1.4	0	0	2	0	0	3.6

%= Percentage of subjects with maternal, fetal and neonatal events of interest

N= Number of subjects with maternal, fetal and neonatal events of interest

Lower and upper limits are exact 95% confidence intervals

**CONFIDENTIAL**207636 (EPI-RSV-008 BOD)  
Protocol Amendment 4 Final**11.3. Cohorts for Analyses (Amended 29-MAY-2020)****11.3.1. Exposed Sets (ES)****11.3.1.1. Pregnant women (mothers)**

The ES will include all pregnant women (mothers) *who signed a valid informed consent form.*

**11.3.1.2. Neonates/Infants**

*Not applicable.*

**11.3.2. Enrolled sets****11.3.2.1. Pregnant women (mothers)**

*The enrolled set will include all pregnant women (mothers) with a valid informed consent who completed Visit 1.*

**11.3.2.2. Neonates/Infants**

*The Enrolled Set will include all neonates/infants*

- born to pregnant women in the enrolled set, and
- Who have a valid ICF signed by the mother/ parent(s) /LAR(s) (as appropriate per local regulations).

**11.3.3. Per Protocol Sets (PPS) (Amended 29-MAY-2020)****11.3.3.1. Pregnant women (mothers)**

The maternal PPS will include all pregnant women (mothers) *in the enrolled set who* meet all eligibility criteria up to the time of their censoring, either at study completion or prematurely as drop-out (e.g. withdrawn consent, lost-to-follow-up).

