## 6.2. Inclusion criteria for enrollment

Deviations from inclusion criteria are not allowed because they can potentially jeopardise the scientific integrity and regulatory acceptability of the study or subject safety. Therefore, adherence to the criteria as specified in the protocol is essential.

All subjects must satisfy ALL the following criteria at study entry:

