**6.3.1. Maternal subjects:**

- Individuals determined to have one of the following conditions associated with increased risk for a serious obstetrical complication (specify any/all that apply in the eCRF)
  - Gestational hypertension;
  - Gestational diabetes uncontrolled by diet and exercise;
  - Pre-eclampsia or eclampsia;
  - Multiple pregnancy;
  - Intrauterine growth restriction;
  - Placenta previa;
  - Polyhydramnios;
  - Oligohydramnios.
- Individuals determined to have (during the current pregnancy) one of the following infections or conditions associated with risk of adverse outcome (specify any/all that apply in the eCRF):
  - Known or suspected:
    - Syphilis infection,
    - Parvovirus B19,
    - Rubella infection,
    - primary genital herpes simplex infection,
    - primary cytomegalovirus infection,
    - varicella infection,

**CONFIDENTIAL**207636 (EPI-RSV-008 BOD)  
Protocol Amendment 4 Final

- Zika infection,
- Active tuberculosis infection,
- Incompetent cervix or cerclage
- Individuals who have any underlying condition or infection that would predispose them to increased risk for a serious obstetrical complication that is not mentioned above.
- Individuals who have behavioral or cognitive impairment or psychiatric disease that, in the opinion of the investigator, could interfere with the subject's ability to participate in the study.
- Individuals who have known or suspected impairment of the immune system, an active autoimmune disorder that is not well-controlled, or who are receiving systemic immunosuppressive therapy.
- Individuals participating in any concurrent clinical trial during the current pregnancy.
- Individuals pregnant with a fetus with a confirmed or suspected major congenital anomaly at the time of enrollment.

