## **8.10. Screening failures**

Screening failures are defined as subjects who withdraw or are withdrawn from the study after giving informed consent, but before study eligibility (presence of all inclusion and absence of all exclusion criteria) is confirmed.

Discovery during screening of any pregnancy related-event of interest or other condition that violates the requirements for study eligibility should be considered a screening failure.

Discovery during Visit 1 of any condition that violates the requirements for study eligibility should also be considered a screening failure.

The development of such conditions (after Visit 1) does not constitute screening failure and should be captured on the eCRF, as applicable.

Limited data for screening failures will be reported to the eCRF. This limited data set is specified in the eCRF.

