**11.3.3.2. Neonates/Infants**

The infant PPS will include all neonates / infants

- *born to pregnant women in the PPS and*
- *who* meet all eligibility criteria up to the time of their censoring, either at study completion or prematurely as drop-out (e.g. withdrawn consent, lost-to-follow-up) who have at least one time point evaluation (see [Table 5](#)).

**CONFIDENTIAL**207636 (EPI-RSV-008 BOD)  
Protocol Amendment 4 Final**11.4. Derived and transformed data**

Age of the infant subject at time of the LRTI case will be expressed in months and will be computed as the difference between the start date of the LRTI case and the date of birth.

Age of the mother at the time of childbirth will be expressed in years and will be computed as the difference between the birth date of the subject and the birth date of the mother.

Duration of the study for each subject will be computed as the difference between the date of last contact (i.e., active or passive surveillance contact or the date of the censoring) and the date when ICF was first signed by the subject / subject's parent[s]/LAR[s]).

All potential LRTI cases identified during the surveillance period will be classified as RTI, LRTI or severe LRTI according to the LRTI case definition and severity scale (refer to [Table 3](#)). The cases will also be classified according to the classification of WHO [[Modjarrad, 2016](#)].

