**11.6. Analysis of primary objectives (Amended 29 May 2020)**

The primary objectives analyses will be performed on the PPS cohorts overall and possibly by region or other relevant grouping. *If there is a difference of 5% or more between the number of participants in the enrolled set and the PPS, primary objectives analyses on the enrolled set will also be performed.*

**CONFIDENTIAL**207636 (EPI-RSV-008 BOD)  
Protocol Amendment 4 Final**In healthy pregnant women with uncomplicated pregnancies at time of enrollment:**

- To determine the frequencies of pregnancy outcomes.  
The number and percentage (with exact 95% CI) of women presenting the following outcomes: live birth, fetal death/stillbirth (antenpartum or intrapartum), and elective/therapeutic termination will be reported for each event by presence or absence of congenital anomalies.
- To determine the frequencies of pregnancy related events of interest as specified in Section [11.1.1.2](#).  
The number and percentage (with exact 95% CI) of pregnant women presenting with the events of interest specified in Section [11.1.1.2](#) will be tabulated for each event within appropriate time windows to be specified in the statistical analysis plan (SAP). Missing data may be considered a separate category.

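### The maternal per-protocol set requires eligibility to hold until censoring, which as written removes women with five of the primary events and conflicts with the rest of the protocol

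*Protocol*

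**What the plan says.** Section 11.3.3.1 builds the maternal PPS from women in the enrolled set who "meet all eligibility criteria up to the time of their censoring, either at study completion or prematurely as drop-out". Section 11.3.3.2 builds the infant PPS from infants "born to pregnant women in the PPS and" who meet their own criteria.

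Section 11.6 makes this the main analysis set: "The primary objectives analyses will be performed on the PPS cohorts overall and possibly by region or other relevant grouping". Section 11.7 does the same for the secondary objectives. The enrolled set is analysed in addition only on a condition: "If there is a difference of 5% or more between the number of participants in the enrolled set and the PPS".

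Section 6.3.1 excludes "Individuals determined to have one of the following conditions associated with increased risk for a serious obstetrical complication". The list opens with "Gestational hypertension" and also names pre-eclampsia or eclampsia, intrauterine growth restriction, polyhydramnios and oligohydramnios. Section 11.1.1.2 lists the same conditions as primary pregnancy-related events from Visit 1 through Visit 6.

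Elsewhere, eligibility belongs to entry. Section 6.2 states: "All subjects must satisfy ALL the following criteria at study entry". Section 6.3 has the exclusion criteria checked at screening and Visit 1. Section 8.10 says of disqualifying conditions: "The development of such conditions (after Visit 1) does not constitute screening failure and should be captured on the eCRF, as applicable".

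**The concern.** In Section 11.3.3.1 the time limit is attached to meeting the criteria, and it runs to study completion or drop-out instead of stopping at entry. A woman who is eligible at Visit 1 and later develops pre-eclampsia then no longer satisfies the rule. She has the outcome, and having it takes her out of the set that measures it.

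The study exists to supply background rates of these events for interpreting later maternal vaccine trials (Sections 1.1 and 1.2). A set that drops the cases gives frequencies of zero for those events. Because the infants of these women go as well, it probably also lowers related neonatal rates such as preterm birth, small for gestational age and low birth weight. A background rate that is too low could make a vaccine look harmful.

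**Working it through.** **1. Overlap of exclusion criteria and primary events**

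| Exclusion criterion (6.3.1) | Primary event (11.1.1.2) |
|---|---|
| Gestational hypertension | Yes, under hypertensive disorders |
| Pre-eclampsia or eclampsia | Yes, under hypertensive disorders |
| Intrauterine growth restriction | Yes, as fetal growth restriction |
| Polyhydramnios | Yes |
| Oligohydramnios | Yes |
| Gestational diabetes, only if not controlled by diet and exercise | Partly |

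Five conditions overlap fully. The inclusion criteria on low-risk pregnancy and good health (6.2.1) could also lapse during follow-up, which would widen the removals.

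**2. The plan's own figures.** Section 11.2 derives evaluable women per country as N × (1 − 0.10): 200 × 0.90 = 180 and 300 × 0.90 = 270. Table 17 gives exact 95% limits. With x cases in n women, lower = the 2.5% quantile of Beta(x, n − x + 1) and upper = the 97.5% quantile of Beta(x + 1, n − x). This reproduces 58 of the 60 limits within 0.1 point. The other two are upper limits at n = 180 with non-integer counts (6.67 against 6.8 at 3%; 3.78 against 3.9 at 1%) and do not affect this point. The planned precision is therefore right for a set that keeps its cases.

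**3. Effect of the literal wording.** The protocol gives no rate for any single event, so the counts below are illustrations inside its 0 to 35% range. Take x women with one of the five conditions out of n before removal. The pooled n is 2,300 × 0.90 = 2,070. The PPS as worded has n − x women and 0 cases. The last column assumes that these are the only removals.

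| n | x | Cases kept: x/n (95% CI) | PPS as worded (95% CI) | Enrolled-set analysis triggered |
|---|---|---|---|---|
| 180 | 5 | 2.8% (0.9 to 6.4) | 0/175 = 0% (0 to 2.1) | No |
| 270 | 13 | 4.8% (2.6 to 8.1) | 0/257 = 0% (0 to 1.4) | No |
| 270 | 27 | 10.0% (6.7 to 14.2) | 0/243 = 0% (0 to 1.5) | Yes |
| 2,070 | 101 | 4.9% (4.0 to 5.9) | 0/1,969 = 0% (0 to 0.2) | No |

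**4. The 5% trigger.** It counts all removals together, not removals per event. An event with a true rate of 4% goes without an enrolled-set result only if all other removals stay below 5 − 4 = 1 percentage point. At 5% or more the enrolled-set analysis is added, and the PPS result remains beside it.

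**5. Infants.** These inputs are assumptions, not protocol figures: preterm risk is 30% in infants of removed mothers and 7% in the rest, and a share q of mothers is removed. The true rate is q × 0.30 + (1 − q) × 0.07, which gives 7.9% at q = 4%, 9.3% at q = 10% and 10.5% at q = 15%. The infant PPS would show 7.0% each time.

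**6. Passages that point the other way.** Section 11.2 deducts only drop-out to reach the evaluable number, which the Glossary equates with inclusion in the per-protocol analysis, and then plans for event percentages of up to 35% in that number. Section 11.6 describes the women as having uncomplicated pregnancies at enrollment and asks for every event in 11.1.1.2 to be tabulated. Neither makes sense if having an event removes a woman.

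**The case against.** The strongest reply is that the protocol already settles the meaning. The Glossary defines eligible as qualified for enrollment. Sections 6.2, 6.3 and 8.10 fix the assessment at entry, and Section 11.2 sizes the study on that footing. The phrase about censoring can be read as saying how long an eligible woman contributes data, which agrees with the rule in Section 10.2 that data up to withdrawal are used. Full literalism also defeats itself: the criteria require a pregnant woman, and at Visit 6, 42 days after delivery, no completer is pregnant.

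Most of this stands as evidence of intent. It does not repair the text. None of those passages defines or overrides the PPS; Section 8.10 governs screening failure and data capture, and the Glossary entry for evaluable refers back to Section 11.3 for its criteria. The sentence in 11.3.3.1 ties the period to meeting the criteria, and an analyst following it would delete cases. Nor is the point simply open for the SAP, because the protocol has fixed a rule from which an SAP using entry eligibility would depart.

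The size of the effect is fairly contested. The 5% trigger is a real, though partial, safeguard, and several conditions together could well reach it.

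**Conclusion.** Wrong as written. The definition of the primary analysis set conflicts with the sections on eligibility, sample size and primary analysis. If applied literally, the PPS frequency of five primary events is 0% by construction, with an exact upper limit of about 1.4 to 2.1% per country in the untriggered examples above, whatever the true rate. Related neonatal rates would probably be biased low, by an amount the protocol's figures do not determine.

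A reader might infer that the study will report no pre-eclampsia or gestational hypertension. The documents do not support that: entry-time eligibility was almost certainly intended, and Section 8.10 has later-onset conditions recorded. A reader might also infer that a 4% event would always be hidden without a back-up analysis. That holds only if all other removals stay below 1 percentage point. Nor does it follow that the enrolled set must become primary or that the 5% trigger must go. Once eligibility is tied to entry, both are ordinary choices.

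**What to change.** Reword Section 11.3.3.1 along these lines: *women in the Enrolled Set who met all eligibility criteria at screening/Visit 1, with data included up to study completion or drop-out; conditions arising after Visit 1 never remove a woman or her infant.* Reword Section 11.3.3.2 to match, with infant eligibility judged at Visit 1-NB.

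No new data or procedures are needed and there is no statistical downside. The cost is the wording change, carried into the SAP.
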